In addition to the above risk factors, other modifications to eligibility criteria have been made in phase 3 to ensure further that at-risk patients are included. Although serological testing for negative serostatus will not be required for study entry, patients who have a known history SARS-CoV-2 infection prior to this study (demonstrated by a positive SARS-CoV-2 serology, antigen, molecular diagnostic test or other diagnostic assay other than the one used for eligibility into this study) will be excluded. Similarly, patients who report or have a known history of COVID-19 any time prior to the current episode of COVID-19 will be excluded.

Inclusion of Patients Under 18 Years of Age

Patients age 0 to <18 years with symptomatic COVID-19 and at least 1 risk factor for severe COVID-19 (defined in Section 7.2.1) will be included in the phase 3 portion of the study as a separate cohort to assess the safety, PK, immunogenicity, and efficacy of REGN10933+REGN10987.

Most children with COVID-19 seem to experience mild disease that can be managed symptomatically in the outpatient setting. However, children with risk factors including underlying medical conditions such as obesity, diabetes, chronic lung disease, or immunosuppression might be at increased risk for severe COVID-19 (Kim, 2020) (Shekerdemian, 2020). Surveillance data reported to CDC through May 2020 indicated that the COVID-19-related hospitalization rate among children 0 to 9 years and 10 to 19 years old with underlying health conditions was approximately 6 times greater compared to children in the same age group with no reported underlying conditions (0 to 9 years, 22.3% versus 3.7%; 10 to 19 years, 14.9% versus 2.3%, respectively), and was similar to the hospitalization rate reported in adults, especially younger adults (eg, 20 to 29 years old), with and without underlying health conditions (17.5% versus 2.7%) (Stokes, 2020). Additionally, according to COVID-NET, a population-based surveillance for laboratory-confirmed COVID-19-associated hospitalizations in 99 counties in 14 states in the US, pediatric patients <12 years accounted for 58.2% of all hospitalized children and adolescents age 12 to 17 years accounted for 42% of all hospitalized children reported to COVID-NET between 1 Mar 2020 to 25 Jul 2020 (Kim, 2020).

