From 25 February 2021 onward, the Sponsor plans to randomize up to approximately 1500 patients 1:1 to either the 1200 mg dose group or the 2400 mg dose group in addition to the patients enrolled under Amendment 6 or 7, to have adequate precision to estimate the difference in the proportion of patients with a COVID-19-related hospitalization or death between the 2 dose groups. For example, assuming an event rate of 1.7% in each group, with a total of approximately 2100 concurrently randomized patients per arm (1744 per arm in mFAS) in 1200 mg and 2400 mg dose groups, a 2-sided 95% confidence interval for the difference will extend approximately 1% from the observed difference. Blinded sample size reestimation may be performed based on the pooled observed event rates.

The EAST v6.0 software was used for sample size calculation.

Phase 3 Cohort 2 and Cohort 3

Up to approximately 180 pediatric patients in cohort 2 is planned with a goal of approximately 52 patients exposed to each dose of study drug, which is considered adequate to describe the drug concentrations over time. In cohort 2, there will be an enrollment of approximately 20 patients <10 kg (10 per treatment group) and 20 patients between \geq 10 kg and <40 kg (10 per treatment group).

In cohort 3, no minimum or maximum enrollment is planned.

Cohorts 2 and 3 will be analyzed descriptively for safety, and may be analyzed descriptively for clinical and virologic outcomes.

Note that cohort 2 and cohort 3 may continue to enroll after enrollment of cohort 1 has been completed.

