5.8. Analysis of Safety Data

The analysis of safety data will be performed on the SAF, as defined in Section 3.2.

The safety analysis will be based on the reported SAEs and AESIs and other safety information (clinical laboratory evaluations and vital signs).

Thresholds for Potential Clinically Significant Values (PCSV) in laboratory variables, vital signs and ECG are defined in Section 10.2.

The summary of safety results will be presented for each treatment group for each cohort.

CONFIDENTIAL

Page 34 of 61

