10.2. Criteria for Potentially Clinically Significant Values (PCSV)

Regeneron Pharmaceuticals, Inc.

Parameter	PCSV	Comments
Total Bilirubin*	>1.5 and \leq 2 ULN and baseline \leq 1.5 ULN* >2 ULN and baseline \leq 2.0 ULN	Must be expressed in ULN, not in µmol/L or mg/L. Categories are cumulative.
		Concept paper on DILI – FDA draft Guidance Oct 2007.
		* At least one level is required, multiple levels are optional for phase 2/3 studies. If it is desirable to get the distribution of significant level, additional shift table on ≤ 1.5 , >1.5 to ≤ 2.0 and > 2.0 category for baseline vs. post baseline may be provided
Conjugated Bilirubin	>35% Total Bilirubin and TBILI>1.5 ULN, and baseline Total Bilirubin \leq 35% or TBILI \leq 1.5 ULN	Conjugated bilirubin determined on a case-by-case basis.
ALT and Total Bilirubin	ALT>3 ULN and TBILI>2 ULN, and baseline ALT \leq 3 ULN or TBILI \leq 2ULN	Concept paper on DILI – FDA draft Guidance Oct 2007.
CPK*	>3 and ≤ 10 ULN and baseline ≤ 3 ULN*	FDA Feb 2005.
	>10 ULN and baseline ≤ 10 ULN	Am J Cardiol April 2006.
		Categories are cumulative.
		* At least one level is required, multiple levels are optional for phase 2/3 studies. If it is desirable to get the distribution of significant level, additional shift table on ≤ 3 , ≥ 3 to ≤ 10 , and ≥ 10 category for baseline vs. post baseline may be provided
Creatinine	\geq 150 µmol/L (Adults) or \geq ULN (if ULN \geq 150 µmol/L) and	Benichou C., 1994.
	baseline < 150 μmol/L or <uln (if="" l)<="" td="" uln≥150="" μmol="">3 independent criteria	</uln>	3 independent criteria
	≥30% change from baseline	
	≥100% change from baseline	

Parameter	PCSV	Comments
Creatinine	<15 ml/min and baseline \geq 15 ml/min (end stage renal	Use is optional.
Clearance	impairment)	FDA draft guidance 2010
(Cockcroft's formula)	\geq 15 -<30 ml/min and baseline \geq 30 ml/min (severe renal impairment)	Four independent criteria, will provide additional shift table if needed
	≥30 - < 60 ml/min and baseline ≥60 ml/min (moderate renal impairment)	
	≥60 - < 90 ml/min and baseline ≥90 ml/min (mild renal impairment)	
Uric Acid		Harrison- Principles of Internal Medicine 17th Ed., 2008.
Hyperuricemia:	>408 μmol/L or >ULN (if ULN≥408 μmol/L) and baseline ≤408 μmol/L or ≤ULN (if ULN≥408 μmol/L)	Two independent criteria
Hypouricemia:	<120 μ mol/L or <lln (if="" <math="" lln≤120="">\mumol/L) and baseline ≥ 120 μmol/L or ≥LLN (if LLN≤120 μmol/L)</lln>	

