WBC	<3.0 Giga/L or <lln (if="" and="" baseline="" giga="" l)="" lln≤3.0="" ≥3.0
Giga/L or ≥LLN (if LLN≤3.0 Giga/L) (Non-Black); <2.0 Giga/L or <lln (if="" and="" baseline="" giga="" l)="" lln≤2.0="" ≥2.0
Giga/L or ≥LLN (if LLN≤2.0 Giga/L) (Black)*</lln></lln>	Increase in WBC: not relevant. *The default criteria. Summary by race (black and Non- black) are optional. To be interpreted only if no differential count available.
	≥16.0 Giga/L or ≥ULN (if ULN≥16.0 Giga/L) and baseline < 16 Giga/L or <uln (if="" giga="" l)<="" td="" uln≥16.0="">	</uln>	
Lymphocytes	>4.0 Giga/L or >ULN (if ULN \geq 4.0 Giga/L) and baseline \leq 4.0 Giga/L or \leq ULN (if ULN \geq 4.0 Giga/L)	
Neutrophils	<1.5 Giga/L or <lln (if="" for="" giga="" l)="" lln≤1.5="" non-black="" or
<1.0 Giga/L or <lln (if="" and="" baseline
≥1.5 Giga/L or ≥LLN (if LLN≤1.5 Giga/L) for Non-Black or ≥1.0 Giga/L or ≥LLN (if LLN≤1.0 Giga/L) for Black*</lln></lln>	International Consensus meeting on drug-induced blood cytopenias, 1991. *The default criteria. By race (black and Non-black) are optional.
	<1.5 Giga/L or <lln (if="" and="" baseline="" giga="" l)="" lln≤1.5="" ≥1.5
Giga/L or ≥LLN (if LLN≤1.5 Giga/L) (Non-Black); <1.0 Giga/L or <lln (if="" and="" baseline="" giga="" l)="" lln≤1.0="" ≥1.0
Giga/L or ≥LLN (if LLN≤1.0 Giga/L) (Black)</lln></lln>	
	<0.5 Giga/L regardless of baseline value or racce	
Monocytes	>0.7 Giga/L or >ULN (if ULN≥0.7 Giga/L) and baseline ≤ 0.7 Giga/L or ≤ULN (if ULN≥0.7 Giga/L)	
Basophils	>0.1 Giga/L or >ULN (if ULN \geq 0.1 Giga/L) and baseline \leq 0.1 Giga/L or \leq ULN (if ULN \geq 0.1 Giga/L)	
Eosinophils	>0.5 Giga/L or >ULN (if ULN≥0.5 Giga/L) and baseline ≤0.5 Giga/L or ≤ULN (if ULN≥0.5 Giga/L)	Harrison- Principles of Internal Medicine 17 th Ed., 2008.

Regeneron Pharmaceuticals, Inc.

CONFIDENTIAL

Parameter	PCSV	Comments
Hemoglobin	\leq 115 g/L or \leq LLN (if LLN \leq 115 g/L) for male or \leq 95 g/L or \leq LLN (if LLN \leq 95 g/L) for female and baseline > 115 g/L or	Three criteria are independent.
	>LLN (if LLN≤115 g/L) for male or >95 g/L or >LLN (if LLN≤95 g/L) for Female*	*The default criteria. By gender (male and female) are optional.
	\leq 115 g/L or \leq LLN (if LLN \leq 115 g/L) and baseline > 115 g/L or >LLN (if LLN \leq 115 g/L) for male;	Criteria based upon decrease from baseline are more relevant than based on absolute value. Other categories for

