Platelets	<100 Giga/L or <lln (if="" and="" baseline="" giga="" l)="" lln≤100="" ≥100
Giga/L or ≥LLN (if LLN≤100 Giga/L)</lln>	International Consensus meeting on drug-induced blood cytopenias, 1991.
	≥700 Giga/L or ≥ULN (if ULN≥700 Giga/L) and baseline < 700 Giga/L or <uln (if="" giga="" l)<="" td="" uln≥700="">Two independent criteria	</uln>	Two independent criteria

Parameter	PCSV	Comments	
Urinalysis			
pН	 ≤4.6 or ≤LLN (if LLN≤4.6) and baseline > 4.6 or >LLN (if LLN≤4.6) ≥8 or ≥ULN (if ULN≥8) and baseline < 8 or <uln (if="" li="" uln≥8)<=""> </uln>	Two independent criteria	
Vital signs			
HR	<45 bpm and decrease from baseline ≥20 bpm ≥120 bpm and increase from baseline≥20 bpm	To be applied for all positions except STANDING	
SBP	≤95 mmHg and decrease from baseline ≥20mmHg ≥160 mmHg and increase from baseline ≥20 mmHg	To be applied for all positions except STANDING	
DBP	≤45 mmHg and decrease from baseline ≥10 mmHg ≥110 mmHg and increase from baseline ≥10 mmHg	To be applied for all positions except STANDING	
Weight	≥ 5% increase from baseline ≥5% decrease from baseline	FDA Feb 2007	

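### SAP Section 10.2 has no laboratory PCSV criteria for patients under 18, and its one-way limits can leave abnormal paediatric values uncounted

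*SAP*

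**What the plan says.** SAP Section 5.8 names one source of thresholds: "Thresholds for Potential Clinically Significant Values (PCSV) in laboratory variables, vital signs and ECG are defined in Section 10.2". It adds: "The summary of safety results will be presented for each treatment group for each cohort". SAP 5.8.2 then commits to a number and percentage of patients with a PCSV for each laboratory test, and Protocol 11.4.5.2 says the same. For vital signs, SAP 5.8.3 plans only descriptive summaries of baseline and change, with plots.

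The cohorts served include children. Protocol 3.2.1.5 describes cohort 2 as "Patients age 0 to <18 years with symptomatic COVID-19" and at least one risk factor. The dose table has weight tiers down to below 2.5 kg. The SAP's sample-size section plans "approximately 20 patients <10 kg (10 per treatment group) and 20 patients between" 10 and 40 kg. Cohort 3 may also include patients under 18.

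Section 10.2 separates some limits by race and some by sex, but none by age. The absolute creatinine limit of 150 µmol/L carries an adult label and has no paediatric counterpart. Creatinine has two further independent criteria: "≥30% change from baseline", and a change of at least 100%. The hyperglycaemia limits (11.1 mmol/L unfasted, 7 mmol/L fasted) are fixed, with no reference to a laboratory limit. Heart rate and blood pressure limits are also fixed.

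**The concern.** Cohort 2's primary objectives include safety and tolerability. Protocol 10.1.1 records only targeted adverse events, and an isolated laboratory abnormality becomes an adverse event only if it is symptomatic, needs treatment or is judged to be one. The laboratory tables are therefore one of the few systematic screens of every child's results.

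That screen uses a table whose one explicit age label says adults. If the fixed cut-offs are kept for a child whose normal range sits well inside them, a value clearly outside the child's range can pass without being counted. The paediatric table would then show fewer PCSVs than the data contain, and nothing in it would tell the reader so.

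**Working it through.** The plan states no figure to reproduce, so the check applies the rules of Section 10.2 as written.

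**1. Which tests are affected.** Protocol 9.2.7 lists 15 chemistry and 10 haematology tests. Carbon dioxide and LDH have no PCSV row, which leaves 25 − 2 = 23.

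- Relative to ULN: ALT, AST, alkaline phosphatase, total bilirubin, CPK and CRP = 6. CRP falls back to a fixed value if no ULN is supplied.
- Fixed cut-off with a ULN or LLN clause: sodium, potassium, chloride, urea nitrogen, albumin, creatinine, haemoglobin, haematocrit, red cells, white cells, platelets, neutrophils, lymphocytes, monocytes, basophils and eosinophils = 16.
- Mixed: glucose = 1. The low side refers to LLN; the high side is fixed.

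Total: 6 + 16 + 1 = 23.

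**2. How the clause works.** A typical row flags a value above a fixed cut-off, or above ULN if ULN is at or beyond that cut-off. I read this as replacement. As a plain either/or it could never change which post-baseline values exceed the limit, so replacement is the reading that gives it a function. Then:

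- high flag = max(fixed cut-off, ULN)
- low flag = min(fixed cut-off, LLN)

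The laboratory limit can only move the flag outward. A ULN below the cut-off, or an LLN above it, is ignored.

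**3. Creatinine.** The documents give no paediatric ranges, so these ULNs are assumptions (µmol/L):

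| Assumed ULN | Flag = max(150, ULN) | Flag / ULN |
|---|---|---|
| 35 | 150 | 150/35 = 4.3 |
| 50 | 150 | 150/50 = 3.0 |
| 70 | 150 | 150/70 = 2.1 |
| 106 | 150 | 150/106 = 1.4 |

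The 30% criterion scales with the child. From assumed baselines of 20, 30 and 50, a rise is flagged at 1.3 × 20 = 26, 1.3 × 30 = 39 and 1.3 × 50 = 65. It cannot see a value already raised at baseline that stays there.

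**4. The low side.** The male haemoglobin low flag is min(115, LLN) g/L. With assumed LLNs of 90, 100 and 110 it moves to 90, 100 and 110. With an assumed LLN of 130 it stays at 115, so values between 115 and 130 are not counted on this criterion. A separate criterion, a fall of at least 20 g/L, also applies.

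**5. Over-flagging.** The lymphocyte high flag is max(4.0, ULN) Giga/L. With assumed ULNs of 6, 9 and 13 it moves to 6, 9 and 13, so no value inside the range is flagged. It stays at 4.0 only if the laboratory reports a ULN at or below 4.0, as it might if adult ranges were applied to children. The documents do not say which ranges are used.

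**6. Weight of one patient.** The SAP aims for about 52 exposed children per dose, so one uncounted patient moves a percentage by 1/52 = 1.9 points. The planned 20 patients below 10 kg are 20/180 = 11% of the cohort maximum.

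**The case against.** The best defence is that Section 10.2 is not simply a list of adult numbers. By step 1, 22 of the 23 tests use a ULN multiple or a ULN/LLN clause, and glucose does so on its low side. PCSV limits are also meant to lie beyond the normal range. Creatinine has its change criteria. Investigators must review every laboratory value. Grade 3 and 4 events are collected for patients under 18, and a by-patient listing with normal range and abnormal flag is planned. All of this stands and limits the harm. It does not supply a paediatric creatinine limit, and it does not make the clause use a child's narrower range.

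A reader might infer four stronger points that the documents do not support.

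- *Normal infant laboratory values will be flagged.* For tests with the clause this follows only if ULN/LLN are adult ranges, which is not stated.
- *Vital signs will be over-flagged.* SAP 5.8.3 names no vital-sign PCSV table. The high heart-rate rule, "≥120 bpm and increase from baseline" of at least 20 bpm, needs both conditions, so a stable value is never flagged.
- *A raised creatinine in a child cannot be flagged.* The change criteria can flag it.
- *Age mix will drive the dose comparison.* The arms under the SAP's design are randomised, the cohort 2 analysis is descriptive, and no safety comparison by weight tier is planned. With few small children, chance imbalance is possible but is not shown.

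**Conclusion.** The point holds in a limited form. The single PCSV table has no criteria for patients under 18. Its absolute creatinine limit is labelled for adults, its hyperglycaemia limits are fixed, and its laboratory clause ignores a child's lower ULN or higher LLN. Abnormal paediatric values can therefore go uncounted.

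The size cannot be fixed from the documents. Under the assumed ULNs, creatinine's absolute limit is 2.1 to 4.3 times ULN, against 1.4 times at the assumed ULN of 106. The change criteria recover part of that loss. The result rests on reading the clause as replacement and on paediatric ranges lying inside the fixed cut-offs for some tests.

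PCSVs are descriptive summary flags, not alerts. They enter none of cohort 2's primary endpoints, which are serious adverse events, infusion-related reactions, hypersensitivity reactions and drug concentrations. The matter should still be corrected, because a stated rule works worse in children and a better one is available from material already in the trial.

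**What to change.** For cohort 2 and for cohort 3 patients under 18, define laboratory PCSV in one of two ways:

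- from the central laboratory's age- and sex-specific ULN/LLN, as multiples of the limit, which Section 10.2 already does for liver enzymes and CPK; or
- as a shift in NCI-CTCAE v5.0 grade, the scale the trial already uses for severity.

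Keep Section 10.2 for adults. State in the SAP that the ULN/LLN used under 18 are age- and sex-specific. Because no vital-sign PCSV table is planned, also state that the Section 10.2 vital-sign cut-offs are not applied to patients under 18.

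The cost is a short SAP appendix edit and some programming. No new data or procedures are needed, since normal ranges are already to be listed. The drawback is that paediatric PCSV counts will not be directly comparable with the adult ones; a table footnote can say so.

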2. INVESTIGATION PLAN

2.1. Study Design and Randomization

This is an adaptive, phase 1/2/3, randomized, double-blinded, placebo-controlled study to evaluate the efficacy, safety, and tolerability of REGN10933+REGN10987 combination therapy in ambulatory patients (ie, outpatients) with early-stage COVID-19.

In phase 1, only symptomatic patients with COVID-19 were enrolled. In phase 2, symptomatic patients and asymptomatic patients were enrolled into separate cohorts. In phase 3, only symptomatic patients are enrolled. The phase 3 patients are enrolled into the following cohorts.

- cohort 1 (\geq 18 years of age, not pregnant at randomization),
- cohort 2 (< 18 years of age, not pregnant at randomization) and
- cohort 3 (pregnant at randomization).

Cohort 1

Prior to protocol amendment 6, patients were randomized in a 1:1:1 allocation ratio to one of the treatments listed below:

- Co-administered REGN10933+REGN10987 combination therapy, 2400 mg (1200 mg each of REGN10933 and REGN10987) IV single dose
- Co-administered REGN10933+REGN10987 combination therapy, 8000 mg (4000 mg each of REGN10933 and REGN10987) IV single dose
- Placebo IV single dose

Randomization was stratified by:

- Presence/absence of COVID-19 symptoms (ie, symptomatic versus asymptomatic cohort). Any asymptomatic patient enrolled are considered to be part of phase 2.
- Country
- Risk factors for severe COVID-19 (no risk factors for severe COVID 19 versus ≥1 risk factor for severe COVID-19).

Starting with Protocol Amendment 6, patients were randomized in a 1:1:1 allocation ratio to one of the treatments listed below, according to a central randomization scheme using an interactive web response system (IWRS) and randomization was stratified by country. The stratification factors for presence/absence of COVID-19 symptoms and risk factors for hospitalization due to COVID-19 were removed because asymptomatic patients and those without risk factors were no longer eligible for the study:

- Co-administered REGN10933+REGN10987 combination therapy, 1200 mg (600 mg each of REGN10933 and REGN10987) IV single dose
- Co-administered REGN10933+REGN10987 combination therapy, 2400 mg (1200 mg each of REGN10933 and REGN10987) IV single dose
- Placebo IV single dose

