The phase 3 sample size of the study is based on having sufficient power to analyze the primary endpoint of proportion of patients with a COVID-19-related hospitalization or all-cause death in the modified full analysis set (mFAS). Based on data from the phase 2 analysis involving the first 799 symptomatic patients enrolled and blinded phase 3 data, the sponsor assumes an event rate of 3.4% for COVID-19-related hospitalization or all-cause death among patients on placebo in the mFAS (patients with at least 1 risk factor for severe COVID-19 and a positive SARS-CoV-2 RT-qPCR test at baseline), and that 83% of all randomized patients (FAS) will have a positive SARS-CoV-2 RT-qPCR test at baseline.

The following table presents estimated number of randomized patients with at least 1 risk factor for severe COVID-19 at each analysis time point for cohort 1 efficacy analysis.

	Placebo FAS ¹ (mFAS)	1200 mg FAS ¹ (mFAS)	2400 mg FAS ¹ (mFAS)	8000 mg FAS ¹ (mFAS)	Total FAS ¹ (mFAS)
Pre-Amendment 6 patients	662 (550)	Not applicable	662 (550)	662 (550)	1986 (1650)
Amendment 6/7 patients randomized by 17 January 2021	841 (698)	841 (698)	841 (698)	Not applicable	2523 (2094)
Final analysis for 2400 mg vs. placebo (patients randomized by 17 January 2021)	1503 (1248)		1503 (1248)		
Interim analysis for 1200 mg vs. placebo (patients randomized by 17 January 2021)	841 (698)	841 (698)			
Amendment 6/7 patients randomized by 24 February 2021	1352 (1122)	1352 (1122)	1352 (1122)	Not applicable	4056 (3366)
Final analysis for 1200 mg vs. placebo (patients randomized by 24 February 2021)	1352 (1122)	1352 (1122)			

Table 2:Estimated sample sizes at each analysis time point for Phase 3 patients with
at least 1 risk factor for severe COVID-19

¹FAS estimates only include those in FAS with ≥ 1 risk factor for severe COVID-19.

The final primary efficacy analysis for the 2400 mg dose group versus placebo comparison will be performed based on patients randomized on or before 17 January 2021, which includes approximately 1503 randomized patients with COVID-19 risk factors per group in the 2400 mg dose group and the placebo group (1248 per group in mFAS). The study will have approximately 76% power to detect a significant treatment effect in the proportion of patients with \geq 1 COVID-19-related hospitalization or all-cause death in mFAS at a 2-sided α of 0.05, assuming 3.4% of

CONFIDENTIAL

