3.1. Efficacy Analysis Sets

Cohort 1

All symptomatic patients from the 800th randomized symptomatic patient will be included in the phase 3 portion of the study. The full analysis set (FAS) includes all randomized patients in phase 3 cohort 1, including those with or without risk factors for severe COVID-19, and is based on the treatment allocated (as randomized).

The modified full analysis set (mFAS) for phase 3 includes all randomized patients with a positive central lab-determined RT-qPCR test from nasopharyngeal (NP) swab samples at randomization, and *with at least one risk factor for severe COVID-19 at baseline*. If pre-dose virologic results from the qualitative test are missing, then results from post-dose sample may be used to determine the qualitative PCR status at baseline, as long as the sample was collected within 2 hours after starting the study drug infusion. The mFAS is based on the treatment allocated (as randomized). The seronegative mFAS is defined as all randomized patients with documented seronegative status (eg, SARS-CoV-2 serum antibody negative) at baseline in the mFAS.

Both mFAS and FAS will be used for the summaries of demographic and baseline characteristics. The mFAS will be used for the analysis of clinical, symptoms, and virologic endpoints. The seronegative mFAS will be used for the analysis of certain virologic endpoints and in analyses of certain clinical endpoints. Data from patients with no risk factors will be summarized descriptively.

For the analyses of 1200 mg group comparing to placebo, only patients concurrently randomized (ie, after Protocol Amendment 6 is implemented) will be included.

Cohort 2

The FAS includes all randomized patients in phase 3 cohort 2 and is based on the treatment allocated (as randomized). The modified full analysis set (mFAS) includes all randomized patients with positive RT-qPCR in NP swab samples at randomization and is based on the treatment allocated (as randomized). If pre-dose results from the qualitative test are missing, then results from post-dose sample may be used to determine the qualitative PCR status at baseline, as long as the sample was collected within 2 hours after starting the study drug infusion. The seronegative mFAS is defined as all randomized patients with documented seronegative status at baseline in the mFAS.

Cohort 3

Data on all patients in Cohort 3 (pregnant population) will be utilized in the analyses.

CONFIDENTIAL

Page 18 of 61

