3.2. Safety (SAF) Analysis Set

The safety analysis set (SAF) includes all randomized patients who received any study drug; it is based on the treatment received (as treated). Determination of "as treated" will be based on the actual study drug received on day 1. Demographic and baseline characteristics, treatment compliance/administration and all clinical safety variables will be analyzed using the SAF.

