4.6.2. Adverse Events of Special Interest

Adverse events of special interest (AESI) are AEs (serious or non-serious) of scientific and medical interest specific to this drug program, for which ongoing monitoring and rapid communication by the investigator to the sponsor will be appropriate.

Treatment-emergent adverse events of special interest for this study are grade ≥ 2 hypersensitivity and grade ≥ 2 infusion-related reactions and any treatment-emergent adverse event that led to a medically-attended visit (phase 3 only), regardless of whether the visit is related to COVID-19.

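### Cohort 1 safety tables compare 1200 mg with all treated placebo patients, without the concurrent-randomisation rule that the SAP applies to efficacy

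*SAP*

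**What the plan says.** SAP 3.2 defines the safety population without any limit by amendment or date: "The safety analysis set (SAF) includes all randomized patients who received any study drug", analysed as treated. SAP 5.8 uses that set and states that "The summary of safety results will be presented for each treatment group for each cohort". SAP 5.8.1 then lists counts and percentages by treatment group, with no between-arm difference or interval.

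For efficacy the SAP is stricter. Section 3.1 says: "For the analyses of 1200 mg group comparing to placebo, only patients concurrently randomized" are included, meaning from Amendment 6 onward. Sections 5.7.1 and 5.7.2 repeat the restriction for the efficacy analyses. The protocol has the same structure: its rule in 11.3.1 refers back to the efficacy sets, and the safety set in 11.3.2 carries no such rule.

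Cohort 1 begins with the 800th symptomatic patient, so it contains patients randomised before Amendment 6 to 2400 mg, 8000 mg or placebo, when there was no 1200 mg arm (SAP 2.1). The full analysis set covers all randomised cohort 1 patients, "including those with or without risk factors for severe COVID-19". From Amendment 6 the stratification factors for symptoms and risk were dropped "because asymptomatic patients and those without risk factors were no longer eligible for the study". Placebo closed on 25 February 2021, while 1200 mg and 2400 mg continued 1:1.

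Protocol 6.1.3.1 says that data from the pre-Amendment-6 patients may need modified or additional analyses, and leaves the details to the SAP. The SAP has no such provision for safety.

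**The concern.** Evaluating safety and tolerability against placebo is a cohort 1 secondary objective (SAP 1.2.2), and the SAP 5.8 tables are where it will be read. With only counts and percentages per arm, readers will compare the 1200 mg and placebo columns directly. Those columns do not cover the same period or the same eligibility criteria. The sponsor has already decided that non-concurrent placebo is unsuitable for 1200 mg efficacy, and the documents give no reason to treat safety differently.

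A second, narrower matter concerns treatment-emergent adverse events that led to any medically-attended visit, which SAP 4.6.2 counts as a phase 3 event of special interest. The documents do not agree on when its collection began. If collection differed between periods, that row would also differ between columns for a reason unrelated to the drug.

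**Working it through.** **Inputs.** SAP Table 2, planning counts of randomised patients with at least one risk factor, per arm:
- Before Amendment 6: 662 each for placebo, 2400 mg and 8000 mg; not applicable for 1200 mg.
- Amendment 6/7 by 17 January 2021: 841 each for placebo, 1200 mg and 2400 mg.
- "Amendment 6/7 patients randomized by 24 February 2021": 1352 each for the same three arms.
- From 25 February 2021: up to about 1500 more, 1:1 between 1200 mg and 2400 mg (SAP 2.2).

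**Reproducing the plan's figures.** 662 + 841 = 1503, as printed. 3 × 662 = 1986 and 3 × 1352 = 4056, as printed. At 83% RT-qPCR positive, 0.83 × 1503 = 1247.5 and 0.83 × 1352 = 1122.2, against 1248 and 1122 printed.

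**Pre-Amendment-6 share of each column.** Share = earlier patients / (earlier + Amendment 6/7 patients).
- Placebo at 24 February: 662 / (662 + 1352) = 662/2014 = 32.9%.
- Placebo at 17 January: 662/1503 = 44.0%. The SAP states this cut for efficacy; SAP 5.8 gives no cut for safety.
- 1200 mg at either date: 0%.
- 2400 mg: the same 662 as placebo, so 32.9% and 44.0%.

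**Post-placebo share of 1200 mg.** Half of 1500 is 750, and 1352 + 750 = 2102. This agrees with the plan's precision calculation "with a total of approximately 2100 concurrently randomized patients per arm". Share = (2100 − 1352)/2100 = 748/2100 = 35.6%. It is a ceiling, because 1500 is a maximum.

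**What the shares do not measure.** All 662 have a risk factor, as do the later patients, so 33% describes calendar time and changed entry criteria, not a risk-factor imbalance. Earlier patients without a risk factor come on top, and their number is not given. Protocol 3.2.1.5 reports phase 1/2 placebo COVID-19 visit rates of 9.2% with a risk factor and 1.9% without. Risk status therefore matters for such visits, but these are efficacy rates and no safety factor can be derived from them.

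**Events leading to a medically-attended visit.** The passages, side by side:
- Protocol Table 4, the schedule for phase 3 before Amendment 6, has adverse-event rows for grade ≥2 infusion reactions, serious events and grade ≥2 hypersensitivity, and none for this event. Table 5 has such a row.
- Protocol 10.1.1 requires the event in all phase 3 cohorts up to day 29, and footnote 7, which the schedules share, names it.
- Protocol 6.1.3.1 moves earlier patients to Table 5 from the point of re-consent, without saying when that was. Under footnote 7, only serious events are recorded from day 30, so re-consent after day 29 would add nothing here.
- The amendment log lists the event among items added under Amendment 7.

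Capture in earlier patients is therefore open. The limiting case can be bounded. Suppose no earlier placebo patient had the event collected, event rates were equal across periods, collection was equal in the concurrent arms, and both columns stop at the same date. The tabulated 1200 mg to placebo ratio is then multiplied by 2014/1352 = 1.49 at 24 February, or 1503/841 = 1.79 at 17 January. If every patient had it collected, the factor is 1.00.

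**The case against.** An all-treated, as-treated safety set with descriptive counts is what both documents specify. No safety test or interval is planned, so no formal inference is at risk. SAP 5.1 also summarises baseline characteristics, including risk-factor status, by arm in the safety set, so readers can see that part of the case mix. The 2400 mg arm has the same pre-Amendment-6 history as placebo, and the safety objective is not dose-specific. All of this stands, and it limits the point to a useful addition. It does not remove it: the baseline table describes the risk-factor mix but does not make the 1200 mg comparison concurrent.

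A reader might infer from the missing Table 4 row that the medically-attended-visit event went uncollected in earlier placebo patients and that the placebo percentage is therefore too low. The documents do not support this. Protocol 10.1.1 and footnote 7 point the other way, and re-consent timing is unknown. A reader might also think that splitting this row at Amendment 6 would cure it. The log places the addition at Amendment 7, so Amendment 6 patients, including those on 1200 mg, may lack it too.

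**Conclusion.** The point holds for 1200 mg versus placebo. By planning counts of randomised patients with a risk factor, 33% of placebo at 24 February 2021 (44% at 17 January) and none of 1200 mg were randomised before Amendment 6. Up to about 36% of 1200 mg was randomised after placebo closed. The safety set will differ from these counts because it is restricted to treated patients and adds earlier patients without a risk factor. The size and direction of the effect on adverse-event percentages cannot be derived from the documents.

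Three stronger readings should be avoided:
- The 33% does not measure a risk-factor imbalance.
- The pre-Amendment-6 imbalance does not touch 2400 mg versus placebo, although later 2400 mg patients also lack concurrent placebo.
- The factor of 1.49 or 1.79 is not an estimate. It is the upper bound among risk-factor patients under the stated assumptions, and it concerns one row only.

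Serious events, grade ≥2 infusion reactions and grade ≥2 hypersensitivity have rows in both schedules, so the three named safety endpoints are exposed only to the period and eligibility differences. No error rate is affected. The change is worth making because the comparison is a stated objective and the remedy is cheap.

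**What to change.** In SAP 5.8, add comparative safety columns for 1200 mg against concurrently randomised placebo (Amendment 6/7 through 24 February 2021), and keep the all-treated columns for exposure.

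For adverse events leading to a medically-attended visit, reconcile Protocol 6.1.3.1, Table 4, section 10.1.1, footnote 7 and SAP 4.6.2 on when collection began. For that row, use as denominator only patients followed on a schedule that collected the event, not a split at Amendment 6.

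The cost is one SAP paragraph and a few table columns, with no new data. The comparative placebo denominator falls from 2014 to 1352 patients with a risk factor at 24 February, so rare events will be estimated less precisely in those columns.
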